2.1.2.6 Potential for fatal infusion reactions

In post marketing studies, rare events of tumor lysis syndrome have been reported in patients who had a high number of circulating malignant cells (>25,000/uL), with a rapid reduction in tumor volume, renal insufficiency, hyperkalemia, hypocalcemia, hyperuricemia, and hyperphosphatemia noted in these patients. For additional details, and updates see current rituximab package insert. In rare cases, severe and fatal cardiopulmonary events, including hypoxia, pulmonary infiltrates, acute respiratory distress syndrome, myocardial infarction, and cardiogenic shock, have occurred. Nearly all-fatal infusion-related events occurred in association with the first infusion.

2.1.2.7 Prevention and management of abrupt increases in serum IgM and viscosity following Rituximab use in patients with WM.

Abrupt and paradoxical increases in IgM levels have been reported with the use of rituximab in patients with WM, which may aggravate hyperviscosity and contribute to hyperviscosity related symptoms. Plasmapheresis is strongly encouraged for those patients at increased risk for hyperviscosity. Rituximab will also be omitted for Cycles 1 and/or 2 as necessary and at the discretion of the Principal Investigator for at risk patients.

2.1.3 Dexamethasone

2.1.3.1 Intravenous Dexamethasone

Each mL of clear, colorless sterile solution contains: dexamethasone sodium phosphate equivalent to dexamethasone phosphate 4 mg (equal to 3.33 mg of dexamethasone or roughly

CONFIDENTIAL

This document is confidential. Do not disclose or use except as authorized.

about 100 mg of hydrocortisone). Non-medicinal ingredients: creatinine, sodium citrate, sodium hydroxide (to adjust pH) and water for injection with sodium bisulfite, methylparaben, and propylparaben are added as preservatives.

2.1.3.2 Oral Dexamethasone

Dexamethasone is commercially available as tablets for oral administration in following potencies: 0.25 mg, 0.5 mg, 0.75 mg, 1 mg, 1.5 mg, 2 mg, 4 mg, and 6 mg. Inactive ingredients are calcium phosphate, lactose, magnesium stearate, and starch.

In the unlikely event of a drug supply interruption, oral dexamethasone will be substituted for IV dexamethasone at same dose used for intravenous administration.

2.1.3.3 Contraindications for Dexamethasone therapy

Dexamethasone will be omitted from therapy while on study in the following circumstances:

- History of tuberculosis or other granulomatous disease;
- Systemic fungal infection;
- History of or development of uncontrollable steroid related glucose intolerance;
- History of or development of steroid related hypersensitivity;
- Intolerance due to gastric and duodenal ulcers despite adequate upper gastrointestinal prophylactic therapy.
- Recipient of a live virus vaccine within 30 days.
- Pregnancy and lactation.
- Development of moderate to severe acute infections.

In the event dexamethasone is omitted, patients will not be removed from study treatment, and will continue to receive all other intended therapy on study.

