3.2 Exclusion Criteria

Patients meeting any of the following exclusion criteria are not to be *enrolled in the study*:

1. Female patients who are lactating or have a positive serum pregnancy test during the screening period.
2. Major surgery within 14 days before enrollment.
3. Central nervous system involvement.
4. Infection requiring systemic antibiotic therapy or other serious infection within 14 days before study enrollment.
5. Evidence of current uncontrolled cardiovascular conditions, including uncontrolled hypertension, uncontrolled cardiac arrhythmias, symptomatic congestive heart failure, unstable angina, or myocardial infarction within the past 6 months.
6. Systemic treatment, within 14 days before the first dose of MLN9708, with strong inhibitors of CYP1A2 (fluvoxamine, enoxacin, ciprofloxacin), strong inhibitors of CYP3A (clarithromycin, telithromycin, itraconazole, voriconazole, ketoconazole, nefazodone, posaconazole) or strong CYP3A inducers (rifampin, rifapentine, rifabutin, carbamazepine, phenytoin, phenobarbital), or use of Ginkgo biloba or St. John's wort.
7. Known hepatitis B or C virus, or human immunodeficiency virus (HIV) infection.
8. Any serious medical or psychiatric illness that could, in the investigator's opinion, potentially interfere with the completion of treatment according to this protocol.
9. Known allergy to any of the study medications, their analogues, or excipients in the various formulations of any agent.
10. Known GI disease or GI procedure that could interfere with the oral absorption or tolerance of ixazomib including difficulty swallowing.
11. Diagnosed or treated for another malignancy within 2 years before study enrollment or previously diagnosed with another malignancy and have any evidence of residual disease. Patients with non-melanoma skin cancer or carcinoma in situ of any type are not excluded if they have undergone complete resection. Male patients with incidental histological findings of prostate cancer (T1a or T1b using the TNM (tumor nodes, metastasis) clinical staging system are not excluded.
12. Participation in other clinical trials, including those with other investigational agents not included in this trial, within 30 days of the start of this trial and throughout the duration of this trial.

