5.2.1.3 Ixazomib Administration

Ixazomib should be administered after dexamethasone each and every cycle, unless dexamethasone is omitted. Please refer to section 2.1.3.3. The order of administration should be dexamethasone followed by ixazomib followed by rituximab.

All protocol-specific criteria for administration of study drug must be met and documented before drug administration. Study drug will be administered or dispensed only to eligible patients under the supervision of the investigator or identified sub-investigator(s). Patients should be monitored for toxicity, as necessary, and doses of **ixazomib** should be modified as needed to accommodate patient tolerance to treatment; this may include symptomatic treatment, dose interruptions, and adjustments of **ixazomib** dose (see Section 6.2).

Capsules of **ixazomib** will also be referred to as study drug. Study drug will be supplied by Millennium as capsules of 2.3, 3.0 and 4.0 mg **ixazomib**. The prescribed administration of **ixazomib** doses in this study is 4 mg **ixazomib** PO once weekly (+/-3 days) on days 1, 8 and 15 in a 28-day cycle during induction therapy, and once on days 1, 8, and 15 in each maintenance cycle.

Patients should be instructed to swallow **ixazomib** capsules whole, with water, and not to break, chew, or open the capsules. Study drug should be taken on an empty stomach (no food or drink) at least 1 hour before or 2 hours after a meal. Each capsule should be swallowed separately with a sip of water. A total of approximately 8 ounces (240 mL) of water should be taken with the capsules.

Missed doses can be taken as soon as the patient remembers if the next scheduled dose is 72 hours or more away. A double dose should not be taken to make up for a missed dose. If the patient vomits after taking a dose, the patient should not repeat the dose but should resume dosing at the time of the next scheduled dose.

Ixazomib drug product is an anti-cancer drug. Refer to the published institutional guidelines regarding the proper handling and disposal of anti-cancer agents.

Investigational **ixazomib** (expired or end of study) should be destroyed on site according to the institution's standard operating procedure. Be sure to document removal and destruction on drug

CONFIDENTIAL

This document is confidential. Do not disclose or use except as authorized.

accountability logs.

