5.2.3.2 Contraindications and Drug interactions for Dexamethasone therapy

Refer to sections 2.1.3.3 and 2.1.3.4 for contra-indications and drug interactions with dexamethasone.

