7.3.6 Contraindications for Dexamethasone therapy

Dexamethasone will be omitted from therapy in the following circumstances:

- History of tuberculosis or other granulomatous disease
- Systemic fungal infection
- History of or development of uncontrollable steroid related glucose intolerance
- History of or development of steroid related hypersensitivity
- Intolerance due to gastric and duodenal ulcers despite adequate upper gastrointestinal prophylactic therapy
- Recipient of a live virus vaccine within 30 days

CONFIDENTIAL

This document is confidential. Do not disclose or use except as authorized.

- Pregnancy and lactation
- Development of moderate to severe acute infections

In the event dexamethasone is omitted, patients will not be removed from study treatment and will continue to receive all other intended therapy on study.

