Sponsor-investigator must also provide Millennium Pharmacovigilance with a copy of all communications with applicable regulatory authorities related to the study product(s), as soon as possible but no later than 4 calendar days of such communication.

SAE and Pregnancy Reporting Contact Information

[contact]

Email: [contact]

Suggested Reporting Form:

- SAE Report Form (provided by Millennium)
- US FDA MedWatch 3500A:
<http://www.fda.gov/Safety/MedWatch/HowToReport/DownloadForms/default.htm>

Procedures for Reporting Drug Exposure During Pregnancy and Birth Events

If a woman becomes pregnant or suspects that she is pregnant while participating in this study **or within 90 days after the last dose**, she must inform the investigator immediately and permanently discontinue study drug. The sponsor-investigator must immediately fax a completed Pregnancy Form to the Millennium Department of Pharmacovigilance or designee (see Section 8.2). The pregnancy must be followed for the final pregnancy outcome.

If a female partner of a male patient becomes pregnant during the male patient's participation in this study, the sponsor-investigator must also immediately fax a completed Pregnancy Form to the Millennium Department of Pharmacovigilance or designee (see Section 8.2). Every effort should be made to follow the pregnancy for the final pregnancy outcome.

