11.6 Pregnancy Reporting

If a woman becomes pregnant or suspects that she is pregnant while participating in this study, she must inform the investigator immediately and permanently discontinue study drug. The sponsor-investigator must immediately fax a completed Pregnancy Form to the Millennium Department of Pharmacovigilance or designee (see Section 11.2). The pregnancy must be followed for the final pregnancy outcome.

If a female partner of a male patient becomes pregnant during the male patient's participation in this study, the sponsor-investigator must also immediately fax a completed Pregnancy Form to the Millennium Department of Pharmacovigilance or designee (see Section 11.2). Every effort should be made to follow the pregnancy for the final pregnancy outcome.

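### The dexamethasone-omission rule (2.1.3.3, 7.3.6) lists pregnancy and then continues all other therapy, contradicting the rule in 11.2 and 11.6 to stop ixazomib permanently

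*Combined protocol and SAP*

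**What the plan says.** **The continuation rule.** Section 2.1.3.3 introduces its list with "Dexamethasone will be omitted from therapy while on study in the following circumstances". The list has eight entries, and one of them is pregnancy together with lactation. The closing sentence says that when dexamethasone is omitted, "patients will not be removed from study treatment, and will continue to receive all other intended therapy on study". Section 7.3.6 has the same eight entries and ends in the same way: "patients will not be removed from study treatment and will continue to receive all other intended therapy on study".

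**The stop rule.** Section 11.2, under the procedures for drug exposure during pregnancy, says of a woman who is or may be pregnant while taking part, or within 90 days after the last dose, that "she must inform the investigator immediately and permanently discontinue study drug". Section 11.6 repeats this for a pregnancy arising "while participating in this study, she must inform the investigator immediately and permanently discontinue study drug".

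**What study drug means.** Section 5.2.1.3 says that capsules of ixazomib "will also be referred to as study drug".

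**Entry.** Exclusion criterion 1 in section 3.2 bars "Female patients who are lactating or have a positive serum pregnancy test during the screening period".

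**The concern.** For a participant who becomes pregnant during treatment, the dexamethasone sections and the adverse event sections give opposite instructions about ixazomib. The first pair says that only dexamethasone is dropped. The second pair says that ixazomib stops for good.

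The protocol itself treats the hazard as real. Section 6.1.4 says that the effect of ixazomib on human pregnancy is unknown. Section 2.1.1.2 reports embryo-fetal toxicity in rabbits at 1 mg/kg and accepts that similar effects in humans are possible. Sections 3.1 and 6.1.4 require contraception or abstinence, with contraception lasting until 90 days after the last dose. A sentence that on its face keeps a pregnant participant on ixazomib does not fit with any of this. What is at stake is participant safety; no estimate or test is affected.

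**Working it through.** The plan states no figure on this point, so the check is a comparison of texts.

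**Step 1: whom does each rule cover?**

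- The list in 2.1.3.3 is expressly for the time on study. Section 7.3.6 does not repeat that limit.
- Criterion 1 in 3.2 keeps out anyone with a positive serum test at screening. Under either section, the pregnancy entry can therefore apply only to a pregnancy found later.
- Sections 11.2 and 11.6 cover a pregnancy that arises during participation. The two groups coincide.

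**Step 2: what does each rule require for that participant?**

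| Agent | 2.1.3.3 and 7.3.6, read literally | 11.2 and 11.6 |
|---|---|---|
| Dexamethasone | Omit | Not addressed |
| Ixazomib (study drug, by 5.2.1.3) | Continue, as part of all other intended therapy | Stop permanently |
| Rituximab (from induction cycle 3) | Continue | Not addressed |

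The ixazomib row cannot be satisfied both ways. The conflict goes no further than that row: section 11 sets no rule for rituximab and none for lactation that begins on study.

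**Step 3: how far does it extend in the text?**

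- Entries in each list: 8. Entries for which another section sets an unconditional, permanent ixazomib stop: 1 (pregnancy).
- Continuation sentences: 2. With an exception or a pointer to section 11: 0.
- Administration sections that cite 2.1.3.3 by number: 2. Section 5.2.1.3 (ixazomib) cites it where dexamethasone is omitted, and 5.2.3.2 (dexamethasone) says "Refer to sections 2.1.3.3 and 2.1.3.4 for contra-indications and drug interactions with dexamethasone". Pointing also to 11.2 or 11.6: 0.

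**Step 4: does another treatment rule settle it?**

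- Pregnancy is not named in the duration criteria (5.4), the ixazomib dose-modification rules (6.2.1) or the withdrawal reasons (7.5).
- The last criterion in 5.4 lets the treating investigator end treatment after a change in the participant's condition. That could cover pregnancy, but it rests on judgement and is not a rule.
- The explicit stop stands only in section 11, which deals with adverse event reporting.
- The study calendar (section 9) schedules the pregnancy test at screening only. Planned induction and maintenance last 24 + 52 = 76 weeks by the durations in 1.1, so a later pregnancy would come to light by self-report or unscheduled testing.

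**The case against.** The best reply is that the closing sentence answers a narrower question. It stands in a dexamethasone section, is conditional on dexamethasone being omitted, and says only that losing this one agent does not end treatment. On that reading, ixazomib stopped under section 11 is no longer intended therapy, and nothing conflicts.

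The literal reading can also be said to prove too much. Acute infection is on the same list, and nobody would take the sentence to override the hold for related Grade 3 toxicity in Table 6-3, the cycle-start criteria in 6.2.1, or removal for progression under 5.4. The stop rule, for its part, is specific, mandatory and stated twice. The references to 2.1.3.3 in section 5 concern the order of dosing and dexamethasone contraindications; they do not ask whether ixazomib should continue.

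Much of this stands. The narrow reading is plausible, the specific rule would probably prevail, and the cross-references are supporting evidence only. Two points remain. First, no text states the narrow reading. Second, pregnancy differs from the other entries. An infection may or may not lead to an ixazomib hold, depending on grade, relatedness and recovery, so continuing other therapy can be correct for that entry. Pregnancy always brings a permanent ixazomib stop, so for that entry the sentence is never correct as worded.

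**Conclusion.** The concern holds. Read literally, 2.1.3.3 and 7.3.6 tell staff to continue ixazomib in a participant who becomes pregnant on study, while 11.2 and 11.6 require it to be stopped permanently. The conclusion rests on taking study drug in section 11 to mean ixazomib, as 5.2.1.3 provides, and on the screening exclusion, which confines both rules to pregnancies found after screening.

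The size is small. The documents do not give the number of women of childbearing potential, so the number of participants at risk cannot be derived. That on-study pregnancy is rare is an assumption, supported by the exclusion, the screening test and the contraception requirement. Actual harm is unlikely because the section 11 rule would probably be followed. Sample size, error rates and the primary analysis do not change. It is an inconsistency in a safety instruction that should be corrected, and it is not a flaw in the statistical design.

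**What to change.** Add the same clause to the continuation sentence in both 2.1.3.3 and 7.3.6: *except in the event of pregnancy, when study drug must be permanently discontinued (see 11.2 and 11.6)*. Sections 11.2 and 11.6 need no change.

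The cost is one clause in each of two mirrored sections, with no added patients, visits or tests. Whether rituximab should also stop in pregnancy, and what to do about lactation that begins on study, are separate decisions for the sponsor; this correction does not settle them.

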2.1.3.4 Drug-Interactions for Dexamethasone

The following drug interactions with dexamethasone have been reported:

- Concurrent administration of dexamethasone with thiazides or furosemide may cause excessive potassium loss.
- Dexamethasone may decrease the effect of anti-muscarinic drugs.
- Dexamethasone may increase the incidence of gastro-intestinal ulceration when administered concurrently with non-steroidal anti-inflammatory drugs.
- Barbiturates, phenytoin, rifampicin, ephedrine, may enhance the metabolism clearance of corticosteroids and reduce the effects of dexamethasone.
- Dexamethasone decreases the serum concentration of salicylates.
- Response to anticoagulants may be altered by dexamethasone.

2.1.3.5 Adverse Events with Dexamethasone

CONFIDENTIAL

This document is confidential. Do not disclose or use except as authorized.

Fluid and electrolyte disturbances: sodium retention; fluid retention; congestive heart failure in susceptible patients; potassium loss; hypokalemic alkalosis; hypertension; hypotension or shock-like reaction.

Musculoskeletal: muscle weakness; steroid myopathy; loss of muscle mass; osteoporosis; vertebral compression fractures; aseptic necrosis of femoral and humeral heads; pathologic fracture of long bones; tendon rupture.

Gastrointestinal: peptic ulcer with possible subsequent perforation and hemorrhage; perforation of the small and large bowel, particularly in patients with inflammatory bowel disease; pancreatitis; abdominal distention; ulcerative esophagitis.

Dermatologic: impaired wound healing; thin fragile skin; petechiae and ecchymoses; erythema; increased sweating; may suppress reactions to skin tests, burning or tingling, especially in the perineal area (after i.v. injection), other cutaneous reactions such as allergic dermatitis, urticaria, angioneurotic edema.

Neurological: convulsions; increased intracranial pressure with papilledema (pseudotumor cerebri) usually after treatment; vertigo; headache; psychic disturbances.

Endocrine: menstrual irregularities; development of cushingoid state; suppression of growth in children; secondary adrenocortical and pituitary unresponsiveness, particularly in times of stress, as in trauma, surgery or illness; decreased carbohydrate tolerance; manifestations of latent diabetes mellitus; increased requirements for insulin or oral hypoglycemic agents in diabetes; hirsutism.

Ophthalmic: posterior subcapsular cataracts; increased intraocular pressure; glaucoma; exophthalmos; retinopathy of prematurity.

Cardiovascular: myocardial rupture following recent myocardial infarction; hypertrophic cardiomyopathy in low birth weight infants.

Metabolic: negative nitrogen balance due to protein catabolism.

Other: anaphylactoid or hypersensitivity reactions, thromboembolism, weight gain, increased appetite, nausea, malaise, hiccups.

The following additional adverse reactions are related to parenteral corticosteroid therapy: rare instances of blindness associated with intralesional therapy around the face and head; hyperpigmentation or hypopigmentation; s.c. and cutaneous atrophy; sterile abscess; post injection flare (following intra-articular use); Charcot-like arthropathy.

2.2 Study Disease

WM is a rare B-cell lymphoproliferative disorder characterized by the uncontrolled accumulation of IgM-producing lymphoplasmacytic cells. The disease was first reported by Jan Waldenström,

CONFIDENTIAL

This document is confidential. Do not disclose or use except as authorized.

who described two patients with a high level of macroglobulin, i.e. pentameric immunoglobulin M (IgM), marked hyperviscosity, typical funduscopic picture and lymphocytoid bone marrow infiltration (Waldenström 1944). Such malignant cells accumulate in the bone marrow, liver, spleen and lymph nodes. WM is diagnosed by the presence of lymphoplasmacytic cells in the bone marrow and an IgM monoclonal spike (M-spike) identified in a serum protein electrophoresis (SPEP) (Owen 2003). The incidence of WM in the United States (US) is approximately 3 per million persons per year accounting for 1000-1500 new cases per year. The clinical course of WM is variable and although patients might experience an overall survival (OS) measured in decades, WM remains incurable with current therapeutic regimens. Hence, the disease course is characterized by continual relapses, each harder to treat than the previous one. Additionally, many of the disabling symptoms associated with the disease, such as hyperviscosity, fatigue, anemia and/or neuropathy, can be exacerbated by our therapy. Hence, the careful evaluation of agents with novel mechanisms of action is needed to improve the quality of life (QOL), and response and survival rates in patients with WM.

2.3 Rationale

Despite advances in the treatment, WM remains incurable and as such; novel therapeutics are needed. Among the first line treatment options for WM are oral alkylators such as chlorambucil, nucleoside analogues, rituximab, alone and in combination treatment, thalidomide, and bortezomib (Trean 2006; Dimopoulos 2008). The use of oral alkylators and nucleoside analogues is associated with risk of myelodysplasia/acute leukemia, disease transformation and stem cell damage thereby limiting their usefulness, particularly in younger stem cell eligible transplant patients (Trean 2009a; Leleu 2009). Rituximab is an important therapeutic, generating overall response rates in 30-40% of patients. Among WM patients receiving rituximab as monotherapy, lower response rates have been observed in those patients with high serum IgM (>6,000 mg/dL) and beta-2 microglobulin (B2M) (>3.0 mg/L) levels, as well as homozygous expression of phenylalanine at amino acid position 158 on CD16 (FcγRIIIA-158) (Trean 2005a; Dimopoulos 2005; Trean 2005b). Limiting the application of rituximab is an idiopathic IgM flare phenomenon, which can provoke symptomatic hyperviscosity, as well as symptomatic IgM related morbidity. Moreover, patients with WM appear to develop earlier intolerance to rituximab versus patients with other indolent lymphomas, which may be related to the frequent presence of auto-IgG antibodies in WM patients.

Bortezomib (Velcade®) is active in WM. As a single agent in relapsed/refractory WM, overall response rates of 40-60% have been reported. In combination with rituximab, higher response rates have been observed in relapsed/refractory or untreated patients (70-80%). The combination of bortezomib with dexamethasone and rituximab (BDR) is particularly active as primary therapy in WM with 96% overall response rate, and VGPR or better categorical responses in 35% of patients. In a recent update at the 6th International Workshop on WM, the projected progression free survival for BDR was estimated at >56 months. An important limitation however to the use of bortezomib is the development of ≥grade 3 peripheral neuropathy in 20-30% of patients using twice a week schedule of administration, and 5-10% with once a week. However, CR rates are potentially lower (5% vs. 20%), and risk of rituximab related IgM flare higher (20% vs. 10%) with attenuation of bortezomib dose to once a week, versus twice a week.

CONFIDENTIAL

This document is confidential. Do not disclose or use except as authorized.

(Treon 2009b; Ghobrial 2010). As such, the identification of novel, neuropathy and stem cell sparing agents is an important goal for therapy of WM.

We recently reported our experience with the combination of carfilzomib (Kyprolis®), dexamethasone and rituximab (CaRD) in 31 proteasome-inhibitor- and rituximab-naïve patients with WM (Treon 2013). Carfilzomib was administered IV on days 1, 2, 8 and 9 every 3 weeks. The median IgM levels declined from 3,510 mg/dL to 1,876 mg/dL, and the median M-protein from 2.09 g/dL to 0.99 g/dL. Median hemoglobin levels improved from 10.6 g/dL to 12 g/dL. Bone marrow tumor burden decreased from a median of 60% to 10%. The ORR was 74% (1 CR, 6 VGPR, 9 PR and 1 MR). The treatment was well tolerated with the only grade 3 or 4 AE of neutropenia (7%). Grade 1 peripheral neuropathy developed in 19% of the patients. There was no grade 2 or higher peripheral neuropathy.

